9.5 Second Step: Comparison of High-dose Ipi vs. HDI

The second step comparison will only occur if the first step comparison described in Section [9.4](#) is significant for either RFS or OS endpoint. In such case, the high-dose Ipi will be compared to HDI. In these comparisons, only the HDI

---

patients enrolled after the low dose ipi arm is added will be included. The same design considerations in Section [9.4](#) will be applied in the second step.

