#### 9.1 Previous Study Design

Initially this study was designed to compare the high-dose (10mg/kg) ipilimumab (Ipi) vs. HDI. The study was activated on May 25, 2011. Subsequently the importance of the low-dose Ipi (3mg/kg) in this patient population was discussed based on the results of the MDX010-20 trial and the FDA approval of ipilimumab at 3 mg/kg in the treatment of metastatic melanoma, leading to the addition of the 3 mg/kg arm to this trial as of January 2012. Since then patients are randomized to three treatment arms: High dose interferon-alfa (HDI), high dose ipilimumab (HIP) and low dose ipilimumab (LIP).

With the addition of low dose ipilimumab (LIP) arm, a two-step hierarchical approach was adopted. In the first step, the high-dose Ipi was to be compared with HDI. If the high-dose Ipi is significantly better than HDI, then the low-dose Ipi was to be compared with HDI as a second step. However, the order of the comparison has been revised to the low-dose Ipi vs. HDI first then to the high-dose Ipi vs. HDI in February 2015. This revision was made since the low-dose Ipi has become the standard of care in the treatment of metastatic melanoma. Since no formal interim analysis had been conducted prior to this revision, this change did not affect the overall type I error rate of the study design.

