## 9.2 Primary Objective

This is a randomized phase III study of high-dose Ipi (HIP) vs. low-dose Ipi (LIP) vs. HDI in patients with resected high-risk melanoma. Approximately 1500 patients will be randomized equally among the three treatment arms, stratified by the AJCC stage (IIIB, IIIC, M1a, M1b). The stratified randomization will be based on the permuted block method.

Rev. 9/14

This study has a two-step hierarchical approach. In the first step, the low-dose Ipi will be compared with HDI. If the low-dose Ipi is significantly better than HDI, then the high-dose Ipi will be compared with HDI as a second step. When comparing the two investigational treatment groups, the primary comparison will be an intent to treat (ITT-defining groups by assigned treatment) analysis of recurrence free survival (RFS; **First Co-primary Endpoint**) and overall survival (OS; **Second Co-primary Endpoint**) in all patients compared to HDI. Both of these endpoints will be used as co-primary endpoints in the sense that the study will be considered a positive study if it meets either one of these 2 endpoints (see Section [1.7.1](#)). That is, in the first step of comparing the low-dose Ipi vs. HDI, it will be a positive study if the low-dose Ipi has better RFS or OS outcome. Then the comparison will proceed to the second step where the high-dose Ipi will be compared to HDI. In each comparison, patients concurrently randomized to the two arms being compared will be included in the analysis. . If high-dose Ipi leads to a better RFS or OS outcome than the HDI, it will be considered as a positive study with respect to the second comparison.

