## 9.3 Sample Size and Accrual

Approximately 1500 patients will be enrolled over 3.3 years. Accrual rate is expected to be 38 per month. Note that the low-dose Ipi arm will be added in January 2012 and the low-dose Ipi arm will need a concurrent HDI arm as control group. Each group has a sample size of about 500 cases. After the low-dose Ipi is added, patients will be still randomized equally to three treatment arms. Accrual to high-dose Ipi arm will be suspended when it reaches 500 cases. For the other two arms (low-dose Ipi and HDI), accrual will continue until each arm has 500 cases since the time of adding the low-dose Ipi arm. This will lead to a slightly larger sample size (> 500) for the HDI arm. However, it is expected that the overall accrual period necessary for completion of the 3mg/kg dose arm and concurrent HDI accrual will not be more than several months due to this adjustment. Every effort will be made to shorten the accrual duration with active intergroup participations. With additional follow up time, a total duration of study is expected to be less than 6 years. The primary comparisons of RFS and OS will be performed using the log-rank test stratified on AJCC stage.

Rev. 9/14

Per amendment #10, approximately 45 adolescent patients (ages 12-17) will be enrolled. If accrual to the adult population reaches its goal before 45 adolescent patients enroll to this study, the study will remain open only to the adolescent population until 2016. If the adolescent population reaches its accrual goal of 45 before the adult population reaches its accrual goal, adolescent accrual will be closed. With the data from a small group (45 or less) of adolescent population, analysis will be mostly descriptive and exploratory.

Rev. 3/15

As of August 15, 2014, adult accrual to Arms A, B, and C has completed. Adolescent patients (ages 12 -17) will be randomized to study arms D, E, and F.

Rev. 9/14

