9.4 First Step: Comparison of Low-dose Ipi vs. HDI

9.4.1 RFS

The recurrence-free survival (RFS) is defined from the time from randomization to the time of disease recurrence or death from any cause.

Since a moderate percentage of long-term cures have been observed in melanoma patients on previous melanoma study, E4697, we have used a model proposed by Berkson and Gage (1952) and Goldman (1984). This model specifies that the target population is a mixture, with proportion  $p$  who will be cured, and  $(1 - p)$  who will fail according to an exponential distribution with rate  $\beta$ . The RFS function  $D(t)$  for the HDI arm (A) and the Ipi arm (B) is expressed as:

$$D_A(t) = p + (1 - p) \exp(-\beta t)$$

$$D_B(t) = \{p + (1 - p) \exp(-\beta t)\}^\theta$$

where  $\theta$  represents a hazard ratio under the proportional hazards alternative. For RFS, it was assumed that the cure rate is 29% and the median survival time for those not cured is 0.487 years in patients randomized to the HDI arm. Under the proportional hazards alternative, we hypothesize that Ipi will reduce the hazard by 25% (hazard ratio  $\theta=0.75$ ). The full information is 655 events in high-dose Ipi and HDI groups. This design provides at least 80% power at a one-sided type I error rate of 0.003. An ITT analysis using the stratified log-rank test will be performed.

9.4.2 OS

Based on E4697 data, the cure rate model is appropriate for this endpoint. This model specifies that the target population is a mixture, with proportion  $p$  who will be cured, and  $(1 - p)$  who will fail according to an exponential distribution with rate  $\beta$ . The survival function  $S(t)$  for the HDI arm (A) and the Ipi arm (B) is expressed as:

$$S_A(t) = p + (1 - p) \exp(-\beta t)$$

$$S_B(t) = \{p + (1 - p) \exp(-\beta t)\}^\theta$$

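### Section 9.5 drops the HDI patients enrolled before the low-dose arm from the high-dose comparison, although Section 9.2 includes them, and still carries over the 9.4 design

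*Combined protocol and SAP*

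**What the plan says.** Section 9.2 sets one population rule for both steps: "In each comparison, patients concurrently randomized to the two arms being compared will be included in the analysis". Section 9.1 supplies the dates. The trial began as HIP vs HDI ("The study was activated on May 25, 2011"), and LIP came later, with the protocol change "leading to the addition of the 3 mg/kg arm to this trial as of January 2012".

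Section 9.3 explains why a restricted HDI group is needed, and the reason concerns LIP only: "the low-dose Ipi arm will need a concurrent HDI arm as control group". It then sets the accrual targets. "Accrual to high-dose Ipi arm will be suspended when it reaches 500 cases", and that count does not restart when LIP joins. For LIP and HDI, "accrual will continue until each arm has 500 cases since the time of adding the low-dose Ipi arm".

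Section 9.5 turns to HIP vs HDI and limits the control arm to those HDI "patients enrolled after the low dose ipi arm is added will be included". It states no matching limit for HIP, gives no reason, and applies the 9.4 design considerations to this step. That design is 1000 patients, 416 deaths for OS at one-sided 0.022, and 655 RFS events at one-sided 0.003, with a hazard ratio of 0.75. Section 9.4.1 even attaches the RFS count to this pair of arms: "The full information is 655 events in high-dose Ipi and HDI groups". The Updated Final Analysis Plan at the head of Section 9 keeps the hierarchy of 9.4 and 9.5 in force.

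**The concern.** HDI patients randomized between May 2011 and January 2012 were allocated against HIP and nothing else. Section 9.2 includes them in HIP vs HDI and Section 9.5 excludes them, so the plan gives two populations for one confirmatory test.

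The consequence depends on how 9.5 is combined with 9.2.

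- **Both rules together.** Early HDI patients are out by 9.5. Early HIP patients then have no concurrent control left in the analysis and go out by 9.2. What remains is a clean randomized comparison, but smaller than the design it borrows.
- **9.5 alone.** All 500 HIP patients face the 500 post-LIP HDI patients. The nominal size is kept. However, early HIP patients have no concurrent controls, and HDI patients randomized after HIP closed are admitted.

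The first costs power. The second gives up part of the randomized contrast.

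**Working it through.** **Inputs.** From 9.4: hazard ratio 0.75; RFS 655 events, one-sided 0.003 (z = 2.748), HDI cure rate 29%, median 0.487 years if not cured; OS 416 deaths, one-sided 0.022 (z = 2.014), HDI cure rate 35%, median 2.44 years if not cured. ln(1/0.75) = 0.2877.

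**Formula.** For equal arms and d events, power = Φ(√(d/4) × 0.2877 − z).

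**The plan's own figures.**
- RFS: √(655/4) = 12.80; 12.80 × 0.2877 − 2.748 = 0.933; power 82.5%. The plan says at least 80%.
- OS: √(416/4) = 10.20; 10.20 × 0.2877 − 2.014 = 0.920; power 82.1% as a fixed design, and 80.4% with the seven planned looks. The plan says 80%.

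Both reproduce. The OS powers below are fixed-design values, so they run slightly high.

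**Patients lost.** No section states the number enrolled before LIP. Appendix XIX.8 gives targets of 600 HDI, 500 HIP and 500 LIP. With 500 HDI counted from LIP's addition (9.3), about 600 − 500 = 100 HDI came earlier. Assuming 1:1 allocation then, about 100 of the 500 HIP did too. I use 100 with an assumed range of 60 to 150. The planned 38 per month over 7.3 to 8.2 months, halved, would give about 138 to 157.

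**Patients per reading, at 100 lost.**
- 9.2 alone: about 500 HIP vs 500 HDI, all concurrent.
- 9.5 with 9.2: about 400 vs 400, all concurrent.
- 9.5 alone: about 500 vs 500, of whom only about 400 vs 400 are concurrent.

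**RFS, 9.5 with 9.2.** Scale events to patients: 655 × 400/500 = 524. √(524/4) = 11.45; 11.45 × 0.2877 − 2.748 = 0.545; power 71%. For 60 and 150 lost, 576 and 458 events give 76% and 63%. Scaling suits RFS because nearly all events on the 9.4.1 curve have occurred by 2019: the curve itself gives 526 events at 400 vs 400.

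**OS, 9.5 with 9.2.** Scaling is too pessimistic here, because deaths continue to accrue. I used the 9.4.2 curve, with the HIP survival function equal to the HDI one raised to 0.75, no loss to follow-up, and a cut-off of 15 February 2019. (The update also prints 2018 once; 2019 is its recommended and planned date.) Post-LIP accrual is uniform from mid-January 2012 and HIP closes when it reaches 500 in all.

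| Lost per arm | Deaths, early pairs dropped | Power | Deaths, early pairs kept | Power |
|---|---|---|---|---|
| 60 | 422 | 83% | 484 | 88% |
| 100 | 386 | 79% | 490 | 88% |
| 150 | 341 | 74% | 497 | 88% |

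Check at 100: √(386/4) = 9.82; 9.82 × 0.2877 − 2.014 = 0.812; 79%. With the pairs kept, √(490/4) = 11.07; 11.07 × 0.2877 − 2.014 = 1.170; 88%.

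**The case against.** The best defence is that 9.2 governs every comparison, so 9.5 must be read with it and the resulting set is determined and unbiased. That stands as far as it goes. A reader might infer that the second-step result would be biased. The documents do not support that: it requires setting 9.2 aside, and even then any bias depends on calendar drift, about which nothing is known.

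A shared post-LIP control period for both doses is also a defensible design, and it would suit the later LIP vs HIP comparison in 9.8.1. The plan does not give this reason, however, and does not state the window for HIP.

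Three further inferences should be resisted.

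- **9.8.1 as a third population rule.** Its wording on including all cases defines analysis by assigned arm, and separates the final data set from the interim cut-offs and from the eligible-and-treated sensitivity analysis. It sets no enrolment window.
- **RFS failing because 655 events become unreachable.** The updated plan fixes a calendar date for all comparisons. On the 9.4.1 cure model the lifetime maximum is only 500 × (0.710 + 0.605) ≈ 657 even at 500 vs 500. That target has almost no slack under any population.
- **OS power of 73%.** This comes from scaling deaths to patients (416 × 400/500 = 333), which ignores follow-up to 2019.

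The number lost is indeed undocumented. Section 9.3 calls the HDI excess slight. At 30 lost per arm, 655 × 470/500 = 616 events would still give about 79% RFS power.

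**Conclusion.** Sections 9.2 and 9.5 conflict on who enters HIP vs HDI. That follows from the text and the dates alone. The window in 9.5 has a stated purpose for LIP and none for HIP.

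Read together, the sections cost efficiency, not validity. At 100 lost per arm, RFS power is about 71% against 82%. OS power is about 79% against about 88% with the early pairs kept; relative to the planned 80%, that OS figure is barely a shortfall. These sizes rest on the inferred count, 1:1 allocation before LIP, uniform accrual and the protocol's survival curves. The true OS level is unknown, because the updated plan expects too few deaths to reach the target.

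The reach is limited. LIP vs HDI is untouched, and HIP vs HDI is tested on an endpoint only if LIP has won on that endpoint. It should be fixed because it is a primary-population rule for a confirmatory test.

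**What to change.** Replace the sentence in 9.5 with:

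> HIP vs HDI includes all patients randomized to HIP or HDI while both arms were open to randomization, from activation onward, and excludes HDI patients randomized while HIP was suspended or closed.

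Keep the post-LIP HDI restriction for LIP vs HDI only. The suspension clause is needed because 9.10.1 records a halt in HIP accrual without saying whether HDI stayed open. The set should come to about 500 vs 500, less any HIP/HDI imbalance from that halt.

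If a post-LIP window is intended for HIP vs HDI, state it for both arms, give the reason, and restate patients, events and power in place of the reference to 9.4.

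The cost is one sentence, applied from randomization dates already held. The sensitive part is timing. Four interim analyses had taken place by September 2018, and 9.10 gives the study statistician access to interim outcomes. The choice should be made and dated before the final analysis, without reference to HIP outcome data.

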#### 9.6 Interim Analysis

First with respect to the first step comparison of low-dose Ipi vs. HDI, interim analyses of RFS and OS will be performed for all semi-annual DMC meetings beginning when approximately 50% of the planned full information (416 deaths among patients treated with low-dose Ipi and HDI) has occurred. The data from both of these co-primary endpoints will be reviewed, however an early stopping of the study will be considered only based on the OS endpoint. It is expected to have 6 interim analyses at .5, .62, .72, .81, .89, .96 information time and 1 final analysis. To preserve the overall type I error rate, critical values at the interim analyses will be determined using a truncated version of the Lan-DeMets spending function corresponding to the O'Brien-Fleming boundary. Boundary values at a nominal significance less than 0.0005 will be truncated at 0.0005, with the boundary also adjusted to preserve the overall one-sided type I error rate of 0.022 for the OS endpoint. This study will also be monitored for early stopping in favor of the null hypothesis. In particular, at each scheduled interim analysis, we will compute the conditional power of rejecting the null hypothesis at full information. If the conditional power is less than 10%, an early termination of the study will be considered.

For the RFS endpoint, interim analysis will begin when the OS endpoint has reached 50% information time and will be repeated every 6 months. The expected information at the first interim analysis is about .83 for the RFS endpoint. Interim analysis of RFS will be presented to the DSMC at the time of OS interim analyses, but the study does not have stopping rules based on the RFS endpoint. The primary analysis for RFS will take place when the full information (655 events) is reached. If a treatment benefit is indicated in the RFS endpoint at this time, this study will be considered as a positive study regardless of the OS result at this time.

The interim analyses for the second step comparison (high-dose ipi vs. HDI) will begin only when the interim analysis for OS or full-information analysis for RFS indicates significantly better result in the low-dose Ipi arm in comparison to the HDI arm.

To preserve overall type I error rates for both RFS and OS endpoints, the hierarchical testing will be implemented separately for RFS and OS endpoints. Interim analyses of low dose Ipi vs. HDI for RFS will begin once low dose Ipi vs. HDI is significant for RFS (and only if it is) and interim analyses of high-dose Ipi vs. HDI for OS will begin once low dose Ipi vs. HDI is significant for OS (and only if it is).

Similarly during the final analysis, if low dose Ipi vs. HDI is significant for RFS at the 0.3% level, then we will compare RFS between high dose Ipi vs. HDI at the 0.3% level. If low dose Ipi vs. HDI is significant for OS at the 2.2% level, then we will compare high dose Ipi vs. HDI at the 2.2% level. These two decisions will be made separately and if only RFS is significant for low dose Ipi vs. HDI, then only RFS will be compared for high dose Ipi vs. HDI. Similarly if only OS is significant to low dose Ipi vs. HDI, then only OS would be compared for the high dose arm.

The futility analysis based on the OS will start at the same time as the first step OS comparison and will continue. At each scheduled interim analysis, we will compute the conditional power of rejecting the null hypothesis at full information. If the conditional power is less than 10%, an early termination of the study will be considered. If the low-dose Ipi arm is suspended due to the futility analysis, the high-dose Ipi vs. HDI comparison will still continue.

## 9.7 Secondary Objectives

### 9.7.1 Toxicity Monitoring

The population for the safety analysis will be comprised of all patients who received at least one dose of study medication. Patients will be monitored for adverse events using the National Cancer Institute's (NCI) v.4.0 of the Common Terminology Criteria for Adverse Events (CTCAE). All treatment-emergent and baseline adverse events and hematological/biochemical toxicities based on laboratory measurements, as well as drug related AE's, will be summarized by treatment group and NCI CTCAE worst grade.

Expected toxicity data for ipilimumab treated patients, based on the BMS four phase II studies utilizing the 10 mg/kg dose with 325 patients, is as follows. Overall 32.6% experienced the worst treatment-related AEs of grade 3/4/5. Immune-related AEs were experienced in 72.3% of patients. Of these, 25.2% were Grade 3/4 and occurred in the following 4 main types: i) Gastrointestinal: e.g., colitis, diarrhea (12.3%), ii) Liver: e.g., transaminase elevation (6.8%), iii) Skin: e.g., rash pruritis (2.8 %), iv) Endocrine: e.g., hypophysitis, thyroiditis (2.5%). Other complications, i.e., bowel perforations, liver failure were minor (~1%). In addition there were 5 treatment-related deaths: 4 immune-related: multi-organ failure, abnormal hepatic function, and acute glomerulonephritis, hypovolemic shock and 1 not immune-related: acute myeloid leukemia. The toxicity data from all treated patients will be reviewed carefully by the ECOG-ACRIN DMC. In the early part of the study, when 50 patients and then 100 patients are treated with each of the ipilimumab doses, toxicity incidence data will be summarized and presented to DMC. All treatment-related toxicity data will be presented along with a summary on the worst grade. A particular attention will be given to the specific toxicity types mentioned above. Toxicity incidence rate and 95% confidence interval for each type will be presented. Upon DMC's review, if there are major issues, this will be communicated with the CTEP.

In the MDX010-20 trial (ipilimumab 3 mg/kg), 97-98% patients experienced any adverse event and approximately 46% experienced grade 3/4/5 adverse events. (Hodi et al. NEJM 2010) The most common adverse events related to the study drugs were immune-related events, which occurred in approximately 60% of the patients treated with ipilimumab. The frequency of grade 3 or 4 immune related adverse events was 10 to 15% in the ipilimumab groups. The most common immune-related adverse event was diarrhea, which occurred at any grade in 27 to 31% of the patients in the ipilimumab groups. The frequency of organ specific grade 3 and 4 adverse events

in the ipilimumab/gp100 and ipilimumab/placebo arms respectively was as follows: dermatologic (2.4% and 1.5% of patients), GI (5.8% and 7.6%), endocrine (1.1% and 3.8%), hepatic (1.1% and 0%). Death due to irAE occurred in 1.3% and 1.5% respectively.

Interim toxicity monitoring and analysis will be performed separately for the high dose ipilimumab (HIP) and low dose ipilimumab (LIP) arms. If one arm meets criteria for discontinuation due to toxicity the other arm will continue enrolling patients and continue to be monitored per protocol monitoring criteria. For example, if HIP arm was discontinued due to toxicity, LIP arm will continue per protocol unless LIP meets criteria for discontinuation as well.

#### 9.7.2 Quality of Life

General hypothesis: There are no clinically relevant differences between the two arms using global QOL scale at the assessed intervals (every 3 months while on treatment and every 6 months off-treatment for one year). There may be a later advantage to the ipilimumab arm if disease progression occurs, thereby leading to a better global QOL.

Primary hypothesis (for sample size calculation): Ipilimumab is superior to HDI using global QOL scale at 12 weeks following the initiation of therapy (after completion of the ipilimumab induction phase).

The primary objective for the QOL study is to evaluate if patients treated with ipilimumab will have a better global QOL. This component of the protocol will be open to patients enrolled by Community Clinical Oncology Programs (CCOPs).

FACT-G will be collected at baseline, every 3 months while on treatment and every 6 months off-treatment for one year. The main time point for the comparison of global QOL between the two treatment arms will be at 3 months following the initiation of therapy (after completion of the ipilimumab induction phase).

FACT-G has four areas of measurements (physical well being, social/family well-being, emotional well-being and functional well-being) with a scale of 0-4. The changes between before and after treatment for each area and summary of all four areas will be compared between the two treatment arms. We do not have the preliminary QOL data to justify the sample size calculation. We plan to perform the QOL study in all patients enrolled by CCOPs, projected to be about a third of the patients (450 total patients, 150 per arm). We will use the baseline and 3 months data to compare the change before and after the treatment between the two treatment arms (high-dose Ipi vs. HDI and low-dose Ipi vs. HDI). If the standardized difference (difference in means / sd) is at least 0.4, this analysis will have at least 80% power for each comparison. Given the exploratory nature of this analysis, no adjustments for the multiple comparisons will be made.

This is based on one-sided type I error rate of 0.025. While the study is open to accrual, the proportion of patients from CCOP institutions will be monitored. If the QOL accrual target cannot be met by CCOPs alone, a plan to expand the QOL component to other institution types will be considered.

The secondary objective of QOL study is to evaluate the effect of adjuvant ipilimumab and HDI on the various symptoms and functioning scales as treatment related side effects that may have an impact on the health-related domains of QOL. FACT-BRM and FACIT-D forms will also be collected on the same schedule as the FACT-G form. FACT-BRM has two additional sections addressing physical and mental QOL aspects. FACIT-D has a section addressing colitis and diarrhea related issues.

For both QOL objectives, ITT analysis in all patients (from two treatments) will be conducted. The changes between before and after treatment will be compared between the two treatment arms. The two-sample t-test will be used to compare continuous measurements and Chi-square test will be used to compare the categorical outcomes between the two treatment groups. Longitudinal regression models will also be used to address the overall change over time during which the QOL data is collected.

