### 5.9 Quality of Life Evaluations

Rev. 2/14

Aspects of quality of life (QOL) will be measured for adult patients enrolled by CCOPS to arms A, B, and C utilizing the FACT-G and FACT-BRM health questionnaires and the FACIT-D (Diarrhea assessment). QOL data will be collected at baseline, every 12 weeks (+/- 2 weeks) while on treatment, at completion of treatment, and every 24 weeks (+/- 2 weeks) while off-treatment for one year. Patients who go off treatment early due to excessive toxicity or progressive disease should complete QOL measures at the specified time points. The calendar should not be reset. Baseline measures are necessary to draw

---

conclusions about the impact of therapy despite the fact that they will have already been altered from predisease levels. They will serve as a comparison for each patient's responses after therapy. The follow-up assessments are included at regular intervals to observe changes in quality of life as treatment unfolds and to determine whether quality of life returns to baseline following the completion of treatment.

- 5.9.1 FACT-G has four areas of measurements—physical well-being, social/family well-being, emotional well-being, and functional well-being—all on a scale of 0 to 4. FACT-BRM has two additional sections addressing physical and mental QOL aspects.
- 5.9.2 Since colitis/diarrhea is one of the main toxicities of ipilimumab, FACIT-D form will be used to assess QOL- related from colitis/diarrhea. FACIT-D form has five areas on physical well-being, social/family well-being, emotional well-being, functional well-being, and additional concerns with a scale of 0 to 4. The last section on additional concerns has detailed questions pertaining to diarrhea. The data items collected in this section will be carefully reviewed. The changes between before and after treatment (for each area and summary of all five areas) will be compared between the two treatment arms.
- 5.9.3 The main comparison will be the change before and after the treatment between the two treatment arms. Longitudinal regression models will also be used to address the overall change over time during which the QOL data is collected.

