- 5.9.9 If a patient fails to complete an assessment for any reason, it will be documented on the Assessment Compliance Form. The patient will still be asked to complete the remaining quality of life assessments.
- 5.9.10 Each CCOP institution will designate an individual who will ensure the timely completion of the quality of life assessments.

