#### 9.8.3 Other secondary analyses

The QOL study is open to patients enrolling from CCOPs. FACT-G, FACIT-D and FACT-BRM forms will be collected every 3 months while on treatment and every 6 months off-treatment for one year.

The main comparison for all forms will be the change in QOL measurements between the baseline and 3 month time point by treatments (high-dose Ipi vs, HDI or low-dose Ipi vs. HDI). Descriptive statistics on QOL measurements will be provided. Two-sample t-test

will be used for each comparison and two-sided p-values will be reported. ITT analysis on all cases with QOL data will be conducted.

At the final analysis, subgroup analyses of the treatment effects on RFS and OS will be conducted. Subgroups by age, sex, ECOG PS, AJCC stage (IIIB, IIIC, M1a, M1b), ulceration status of the primary, type of lymph node involvement (microscopic / macroscopic), extent of lymph node involvement (1 vs 2-3 vs  $\geq 4$  positive LN) will be considered in the ITT patient population. This analysis will be summarized using the forest plots with HRs and 95% CIs.

In the event of missing data, it will be assumed that the data will be missing at random and no imputation will be performed.

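### The main 3-month quality-of-life test is an unadjusted t-test on change: less precise than baseline adjustment, and not valid in general under the plan's own missing-at-random assumption

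*Combined protocol and SAP*

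**What the plan says.** Section 9.7.2 sets the main time point at 3 months and bases the comparison on two values per patient: "We will use the baseline and 3 months data to compare the change before and after the treatment between the two treatment arms". The method follows in the same section: "The two-sample t-test will be used to compare continuous measurements and Chi-square test will be used to compare the categorical outcomes". Section 5.9.3 agrees: "The main comparison will be the change before and after the treatment between the two treatment arms". Section 9.8.3 extends the 3-month change comparison to all three forms (FACT-G, FACT-BRM and FACIT-D) and defines the analysis set: "ITT analysis on all cases with QOL data will be conducted". It ends: "In the event of missing data, it will be assumed that the data will be missing at random and no imputation will be performed".

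No covariate is named for this comparison, although section 9.2 says that randomization is "stratified by the AJCC stage (IIIB, IIIC, M1a, M1b"). Sections 5.9.3 and 9.7.2 add longitudinal regression models, but as a further analysis of the whole course over time. Their type, covariates and handling of baseline are not given, and they are not assigned to the 3-month comparison.

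For sample size, section 9.7.2 projects 150 patients per arm and claims at least 80% power for a standardized difference of 0.4 at one-sided 0.025. It says that no preliminary quality-of-life data exist, calls the analysis exploratory, and allows for a shortfall: "If the QOL accrual target cannot be met by CCOPs alone", other types of institution may be brought in.

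**The concern.** There are two separate weaknesses.

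**Precision.** A change score uses the baseline but fixes its slope at 1. The fitted slope is usually smaller, so the change score carries avoidable noise. The test also ignores the randomization stratum.

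**Match between test and assumption.** Missing at random lets the chance of a missing 3-month form depend on observed data, including baseline score and arm. A complete-case t-test on change needs more than that. It is unbiased if forms are missing completely at random, if missingness depends on arm alone, or if it depends on baseline in the same way in both arms. It is biased if the dependence on baseline differs by arm. The regimens differ in route, schedule and toxicity, so that pattern cannot be ruled out.

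At stake is the main result of a listed secondary endpoint (section 2.2.2) that has a superiority hypothesis. The trial's definition of a positive study (section 1.7.1) is not affected.

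**Working it through.** **Inputs.** From section 9.7.2: 150 per arm, standardized difference 0.4, one-sided 0.025. The documents give neither the baseline-to-3-month correlation (rho) nor a missing rate. Both are assumed below and varied.

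**1. The plan's own figure.** Two-sample t-test (noncentral t), d = 0.4, 150 per arm: power 93.2%. The first n with at least 80% power is 100 pairs per arm (80.4%; 99 gives just under 80%). The claim of at least 80% is met, and it survives the loss of about a third of pairs (50/150).

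**2. Precision.** With s the SD of a single score:
- change score variance: 2s²(1 − rho)
- ANCOVA variance: s²(1 − rho²)
- ratio: (1 + rho)/2

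| rho | ratio | pairs per arm for 80% power (100 × ratio) |
|---|---|---|
| 0.4 | 0.70 | 70 |
| 0.5 | 0.75 | 75 |
| 0.6 | 0.80 | 80 |
| 0.7 | 0.85 | 85 |
| 0.8 | 0.90 | 90 |

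These counts read 0.4 as SD of change, the natural reading for a change-score test. If it meant the SD of a single score, the t-test would need 119, 100 and 60 pairs at rho 0.4, 0.5 and 0.7, and ANCOVA 84, 75 and 52.

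**3. Bias with no true effect, missingness depending on baseline and arm.** Take standardized bivariate normal scores. A patient with baseline x has expected change −(1 − rho)x. So the bias (ipilimumab minus HDI) is −(1 − rho) times the difference in mean baseline between the completers of the two arms.

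*Scenario A:* HDI missing 30% below and 10% above the median baseline; ipilimumab missing 15% throughout. The mean of each normal half is ±0.798.
- HDI completers' mean baseline: 0.798 × (0.9 − 0.7)/(0.9 + 0.7) = 0.100. Ipilimumab completers: 0.
- Bias: 0.100 × (1 − rho) = 0.060, 0.050 and 0.030 SD at rho 0.4, 0.5 and 0.7, in favour of ipilimumab.
- Error at rho 0.5: SD of change = 1. Completers number 150 × 0.80 = 120 and 150 × 0.85 = 127.5. SE = √(1/120 + 1/127.5) = 0.127. Shift = 0.050/0.127 = 0.39. P(Z > 1.96 − 0.39) ≈ 5.8%.

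A simulation of 20,000 trials with 150 per arm gave bias 0.061, 0.049 and 0.030, and one-sided error 6.6%, 5.9% and 4.9%. ANCOVA bias was at most 0.0012 SD, with two-sided error 4.9% to 5.1%.

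*Scenario B:* HDI missing 40%/10%. Completers' mean is 0.798 × (0.9 − 0.6)/(0.9 + 0.6) = 0.160, so bias is 0.096, 0.080 and 0.048 SD (simulated 0.098, 0.079, 0.048).

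*Patterns that do no harm:* 20% missing completely at random in both arms, or 30%/10% in both arms, gave t-test bias of at most about 0.001 SD and two-sided error 4.7% to 5.1%. Different rates by arm with no dependence on baseline (30% against 15%) also gave no bias.

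**4. Missingness that follows the 3-month score itself** (outside missing at random; rho 0.5; HDI 30%/10% to 40%/10%). Change-score bias is −0.05 to −0.08 SD. ANCOVA bias is −0.07 to −0.12 SD.

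**The case against.** The strongest reply is that nothing the plan claims fails. The endpoint is secondary and exploratory, the t-test exceeds its stated power, and a change score is familiar and easy to read. All of that stands, and it limits the weight of the point.

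The plan also works to prevent missing data. Section 5.9 asks for forms after early discontinuation, provides for mailing and telephone follow-up, and records reasons: "If a patient fails to complete an assessment for any reason, it will be documented on the Assessment Compliance Form". Section 9.7.2 monitors enrolment and can widen it. These steps reduce the exposure but cannot guarantee that it is nil.

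The bias needs a particular pattern, and its size follows the assumed rates. A steeper dependence on baseline (a logistic model with about 30% missing overall on HDI and a random 15% on ipilimumab) gave 0.13 SD of change and 16.3% error at rho 0.5. No single figure is therefore a property of this trial. What stands is the qualitative result that missing at random does not by itself justify the test.

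ANCOVA is the more biased of the two when missingness follows the 3-month score, which is the likelier pattern if toxicity drives it. That is correct, and it is why a sensitivity analysis belongs in the fix.

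Finally, longitudinal models are already planned, and a likelihood-based one with baseline included could be valid under missing at random. As written they are unspecified and do not supply the main 3-month result. The benefit of adjusting for stage is not quantified; stage is included because it stratified randomization.

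**Conclusion.** The concern holds. The main 3-month comparison is an unadjusted t-test on change scores in patients with both values. Its variance exceeds that of ANCOVA by a factor of 1/0.90 to 1/0.70 over assumed correlations of 0.8 to 0.4, and missing at random does not by itself make it valid.

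The efficiency loss does not threaten the stated power at 150 per arm. It matters if enrolment or completion falls short: at 100 pairs per arm the t-test is at about 80% power, while ANCOVA is at about 92% to 85% for rho 0.4 to 0.8, with the effect in SD-of-change units. The bias in the moderate scenario is small beside the 0.4 SD design effect, but it doubles or more the nominal 2.5% error. Every bias figure rests on assumed correlations and missing rates.

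This is a recommended improvement to a secondary analysis. It does not affect the trial's primary conclusions.

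**What to change.** - Make the main 3-month analysis an ANCOVA of the 3-month FACT-G score on arm, baseline score and AJCC stage. Alternatively, use a likelihood-based repeated-measures model with baseline, arm, visit, arm-by-visit and stage, and report the 3-month contrast.
- Apply the same model to FACT-BRM and FACIT-D, and keep the change-score t-test as supportive.
- State which variables the missing-at-random assumption conditions on. If missingness is expected to depend on observed toxicity or recurrence, baseline alone is not enough; those variables need to enter the likelihood-based model or a multiple-imputation model.
- Add a missing-not-at-random sensitivity analysis, for example arm-specific delta-adjusted multiple imputation with a tipping point.
- Report missing 3-month forms and their reasons by arm, from the Assessment Compliance Form.
- State whether the 0.4 refers to the SD of change or of a single score.

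The cost is SAP wording and minor programming. Baseline, stage and reasons for missing forms are already collected, so no extra data or patients are needed.
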